## **5 INVESTIGATIONAL PRODUCT**

The drug combination P2B001 is comprised of two drugs; pramipexole and rasagiline, both currently approved drugs and routinely used in standard therapy for early PD. Each active pharmaceutical ingredient (API) is formulated separately as extended-release pellets (i.e., inert sugar bead core layered with drug and covered with an extended release coating). The two types of pellets are packed into a capsule to provide the desired dose.

Pramipexole is a non-ergot, specific and selective dopamine receptor agonist of the dopamine D2 subfamily (Perez-Lloret S, 2010), currently marketed as immediate release and as extended release. Rasagiline is a selective and irreversible monoamine oxidase B (MAO-B) inhibitor (Youdim MB, 2001). Thus, while pramipexole compensates for the lack of endogenous neurotransmitters by activating the postsynaptic dopamine receptor, rasagiline causes an enhancement of synaptic dopamine levels by inhibiting dopamine oxidative metabolism.

Pramipexole is currently marketed as immediate release and as extended release (ER). In this study the ER product will be used as a calibration arm. The starting dose of pramipexole ER is 0.375 mg given once per day. Based on efficacy and tolerability, dosages may be increased gradually, not more frequently than every 5 to 7 days, first to 0.75 mg per day and then by 0.75

mg increments up to a maximum recommended dose of 4.5 mg per day (Summary Basis of Approval NDA 20667., 1997).

Rasagiline is only marketed as immediate release. The recommended monotherapy dose of rasagiline is 1 mg once daily ( Azilect Label, 2010).

## 5.1 Dosage

The dosage for the three main study arms will be:

- P2B001 (pramipexole dihydrochloride 0.6 mg/rasagiline 0.75 mg) once daily
- Pramipexole dihydrochloride (0.6 mg) once daily
- Rasagiline (0.75 mg) once daily

The dosage for the calibration arm will be:

- Pramipexole ER individually titrated to an optimal dose (1.5-4.5mg/day).

The combination product (P2B001) and its individual components, pramipexole and rasagiline were produced by: Catalent Pharma solutions Somerset, USA address: [name].

The pramipexole ER comparator and its placebo tablets were produced by:  
[name] Limited, [name]

## 5.2 Dose Modification

Subjects may be allowed to miss a dose of study medication if:

- 1) Subject develops an adverse event that the Investigator believes requires the subject's dose to be held temporarily, or
- 2) Subject loses their kit of study medication and a replacement kit is requested, in this situation the PI should request an emergency shipment to alert the distributor to ship the replacement kit urgently).

During the pramipexole ER titration phase, the PI or sub-Investigator may modify (up or down) subject's dose to either 1.5, 3.0 or 4.5 mg of the pramipexole ER/identical placebo to reach the optimal tolerated therapeutic dose. Following the titration phase, after week 6, no modifications are allowed.

If the subject experiences intolerable adverse events, dosing may be held temporarily or withdrawn (all treatments, including both capsules and tablets, please note that pramipexole

ER/matching placebo tablets need to be down titrated gradually (see down titration instructions in section 6.1). However, the subject will continue to be followed-up according to the protocol pre-planned schedule of activities

No other dose modifications will be allowed in this study.

### **5.3 Method of Administration & Meals**

Subjects will take the study medications (capsule and tablets) by mouth with a glass of water (8oz or 240ml). Study medication can be taken with or without food and efforts should be made to take the study medication at about the same time every day.

## **6 STUDY DESIGN**

### **6.1 Overall Study Design and Plan Description**

This study is a phase 3, twelve-week, randomized, double-blind, double-dummy, 4-arm, parallel group, multi-center, multinational study to determine the efficacy, safety and tolerability of P2B001 in subjects with early Parkinson's disease as compared to its individual components and compared to a calibration arm of pramipexole ER.

Up to 525 eligible subjects with early untreated PD, who are not early terminated from the study during screening or baseline visits and are randomized to treatment with P2B001 0.6/0.75 or pramipexole 0.6 mg once daily, or rasagiline 0.75 mg once daily, or pramipexole ER titrated to optimal dose (1.5, 3.0 or 4.5mg) using a randomization scheme of 2:2:2:1, respectively. Randomization will take place following the completion of all screening procedures including subject approval by both site PI and the central EMC. Subjects will be recruited from approximately 70 sites in North America and Europe.

Each subject will be asked to take one capsule and 1-3 tablets once daily. The capsules will contain either P2B001 0.6/0.75 mg or pramipexole 0.6 mg or rasagiline 0.75 mg or matching placebo. The tablets will contain either Pramipexole ER or matching placebo.

Dosing Regimen:

- P2B001 pramipexole dihydrochloride 0.6mg/Rasagiline 0.75 mg Once Daily + Placebo of Pramipexole ER.
- Pramipexole dihydrochloride 0.6 mg Once Daily (PPX 0.6) + Placebo of Pramipexole ER.

- Rasagiline 0.75 mg Once Daily (RAS 0.75) + Placebo of Pramipexole ER.
- Pramipexole ER individually titrated to optimal dose + Placebo of P2B001.

Study Structure:

- Up-titration phase
- Maintenance phase
- Down-titration phase
- Safety follow-up phase.

[figure not shown]
[figure not shown]
Up-Titration phase: A 3-6 week double blind, double dummy titration phase with pramipexole ER or matching placebo. During this phase subjects will also take 1 capsule of P2B001/RAS 0.75/PPX0.6/Placebo which does not need titration. For the first 3 weeks the titration of the pramipexole ER will be increased by weekly increments up to a daily dose of 1.5 mg as follows: 0.375, 0.75 and 1.5 mg. If needed, between weeks 3 and 6, the titration can continue to a daily dose of 3.0 mg or 4.5 mg of pramipexole ER or matching placebo or reduced to a minimum of 1.5mg with the final level determined based on achieving satisfactory efficacy and tolerability. On completion of the dose-titration phase (end of week 6), the minimum therapeutic dose of Pramipexole ER 1.5 mg per day (or placebo) must be achieved by all the patients. The treatment with study medications of patients who cannot achieve this dosage will be discontinued, but the subject will be requested to continue with all the study visits.

Maintenance phase: Once the final dose level has been reached for the pramipexole ER, the subject will continue at that dose, together with the once daily P2B001/RAS 0.75/PPX0.6/Placebo capsule, until the end of Week 12.

Down-titration phase: a 7-day gradual down titration of pramipexole ER or matching placebo. The down titration should be done by reducing the dose every two days by half (except for subjects taking 4.5 mg, these should reduce the dose to 3.0 mg and then continue to reduce by half every two days). There is no treatment with once daily P2B001/RAS 0.75/PPX0.6/Placebo capsules during this period.

Safety follow-up phase: a 7 days period of no treatment of pramipexole ER and 14-day period of no treatment for the P2B001/RAS 0.75/PPX0.6/Placebo capsule.

**Study design scheme:**

\*Titration phase: Subjects can stop titration of pramipexole ER or placebo at 1.5 mg or can continue titration and increase the dose to 3.0 or 4.5 mg to optimal dose or decrease back to 3.0 or 1.5 mg. The dosage level achieved at the end of the titration phase (end of week 6) is then held constant during the maintenance phase ending at the end of week 12.

## **6.2 Rationale for Study Design, study population and Doses**

The study is designed to show the contribution of both active components, pramipexole and rasagiline, to the efficacy of the combination product P2B001 by comparing the efficacy between P2B001 and its individual components as the co-primary objectives. In addition, the study includes a calibration arm in order to characterize the benefits of P2B001 in respect to safety and efficacy of currently used therapeutic doses of pramipexole ER.

Early Parkinson's disease patients are chosen for this study, since they are the patient population that most likely can benefit from the combination product. The use of the combination product can delay the beginning of treatment with L-DOPA and as consequence reduce and delay the risk of developing motor complications with L-DOPA treatment.

The study was adequately powered to allow demonstration of the efficacy of P2B001 over its 2 components by randomly allocating 150 subjects to each of P2B001 arms and its 2 components. Additional 75 subjects will also be randomized to treatment with pramipexole ER to allow characterization of the benefits of P2B001 with reference to pramipexole ER titrated to individual optimal doses.

The dose of P2B001 chosen for this study is based on the results of the previous phase 2b dose ranging study (P2B001/001). Both doses of P2B001 that were tested (0.6 mg pramipexole/0.75 mg rasagiline and 0.3 mg pramipexole/0.75 mg rasagiline) provided significant clinical benefits with a good safety profile. The 0.6 mg pramipexole/0.75 mg rasagiline dose was chosen because there was consistent numerical benefit for this dose on total, motor and ADL UPDRS scores, PDQ39 and CGI-severity assessments. Both doses were well tolerated with an adverse event profile similar to placebo, with the exception of somnolence and mild nausea, known adverse events of pramipexole. Slightly more cases of somnolence and nausea were reported for the 0.6 mg pramipexole/0.75 mg rasagiline dose, but both doses did not show statistically significant differences from placebo in the ESS scale and the reports of nausea in both doses were mostly mild and transient.

Subjects with mild to moderate renal impairment and subjects with mild hepatic impairment were included in the previous phase 2b study and were followed up with monthly renal and liver function tests to assure compliance with exclusion criteria 17 and 18 and these showed no significant changes. In the current study subjects with mild renal and or mild hepatic impairment will also be included with the same additional follow up to assure compliance with exclusion criteria 17 and 18. In case of worsening in a subject's liver or renal condition and the subject is not compliant with the above exclusion criteria, their participation in the study will be stopped.

Subjects with moderate renal impairment (creatinine clearance between 30 and 50 mL/min) will be excluded in the current study due to possible titration of pramipexole ER tablets to doses above the recommended dose in such patient populations, which is 2.25mg/day.

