#### Early Treatment Termination (ETT)

A subject who discontinued study medication for any reason before the end of week 12 will continue pre-planned study schedule of activities as follow up. The subject will be requested to undergo a treatment termination visit as described in section 9.2.11

Please note that P2B001/PPX 0.6/RAS 0.75/Placebo capsules can be stopped immediately, while pramipexole ER/matching placebo tablets need to be gradually down titrated as described in section 6.1.

The reasons for withdrawal could include the following:

- Subject withdrawal of consent to be treated with study medication(s) but still consenting to participate in study visits and activities
- Request of the Investigator for any medical or other reason
- Request of the primary care physician via the Investigator
- Pregnancy
- Non-compliance
- Subject who cannot achieve the minimum therapeutic dose of pramipexole ER (or placebo) of 1.5 mg per day.
- Major protocol violation
- Adverse Event/Experience
- Lack of Efficacy
- Subjects who, according to the Investigator, need additional therapy that is excluded in the protocol for the treatment of the disease.
- Any other reason relating to the patient's safety or integrity of the study data.

If a subject suspect that she is pregnant, a urine test will be performed at the site. If the urine test is positive, study drug administration will be interrupted pending the results of a confirmatory blood/serum test. If the pregnancy is confirmed with a positive blood/serum test, then the subject will be permanently discontinued from study drug, but should participate in a Treatment Termination visit and continue with all the study visits as follow up visits up to and including safety follow up visit at week 14. The PI will follow the subject until she has given birth.

On completion of the dose-titration phase (end of week 6), the minimum therapeutic dose of pramipexole ER 1.5 mg per day (or placebo) must be achieved by all the patients. The treatment with study medications of patients who cannot achieve this dosage will be discontinued, but the subject will be requested to continue with all the study visits.

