#### Early Study Termination (EST)

A subject who requests to stop study participation for any reason before the end of week 12, including study treatment and study scheduled activities, will be requested to undergo a study termination visit as described in section 9.2.11, unless erroneously randomized or withdrew consent prior to first dose.

The reasons for EST could include the following:

- Pregnancy
- Adverse Event/Experience

- Subject withdrawal of consent and refusal to continue participation in study due to lack of efficacy or due to other reasons
- Lost to follow-up/failure to return
- Death
- Erroneously randomized
- Withdrew consent prior to first dose

If there is a medical reason for withdrawal and the subject refuses to come to study visits after study medication was stopped, the subject will remain under the supervision of the PI as long as the PI deems medically necessary.

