### **9.2.11 Early Treatment/Study Termination Visit**

Subjects who terminate treatment/study early (following first dose and prior to visit 6) according to criteria in section 7.5 will be requested to undergo a treatment/study termination visit. The treatment termination visit can be conducted as part of the next scheduled study visit if it is within 5 days of treatment termination. If the next scheduled visit is more than 5 days away it is preferable, if possible, to schedule an “unscheduled” visit as soon as possible. All efforts should be made to schedule the early treatment/study termination visit as close to the treatment/study termination as possible. **All activities listed in the treatment termination (visit 6) and safety visits (visit 7) will be performed at this visit.** The entire study medication kit with all boxes and bottles left should be returned. The date and reason for the ETT and any data generated from the ETT visit will be documented in the eCRF.

Subject will be requested to continue all study schedule activities as in section 9.2.11.1. If a subject refuses to take part in the scheduled study visits and activities it will be documented as early study termination and the Investigator shall only follow up on any safety issues if needed.

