#### ***9.2.11.1 Follow-up visits of subjects that have terminated the study treatment early***

ETT subjects will be requested to continue with all study visits and activities as planned, for follow up, without taking any study medication. During these visits, all questionnaires and assessments will continue as planned for follow up. Accountability will be omitted since study drug was returned at the ETT visit.

Subjects may take rescue therapy during the follow-up visits; this will be documented in the concomitant medication list.

ETT subjects that decided later to stop their participation in the study will be requested to undergo a study termination visit. **All activities listed in the treatment termination (visit 6) and safety visits (visit 7) will be performed at this visit.**

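### Section 6.2 stops study participation when renal or hepatic function worsens, but Sections 7.5, 9.2.11 and 9.2.11.1 keep subjects who come off drug on their scheduled visits (low priority)

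*Protocol*

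**What the plan says.** Section 6.2 explains that subjects with mild renal or mild hepatic impairment are enrolled with extra monitoring against exclusions 17 and 18. Appendix I places the extra tests at Visits 4 and 5 (weeks 5 and 8). Where liver or renal function worsens and "the subject is not compliant with the above exclusion criteria, their participation in the study will be stopped". The sentence does not refer to ETT.

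Section 7.5 separates ETT from early study termination (EST):

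- **ETT:** "A subject who discontinued study medication for any reason before the end of week 12 will continue pre-planned study schedule of activities". The listed reasons include "Request of the Investigator for any medical or other reason", an adverse event, and anything else bearing on the patient's safety.
- **EST:** "A subject who requests to stop study participation for any reason before the end of week 12, including study treatment and study scheduled activities".

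Section 9.2.11 asks for a termination visit under either route: "All activities listed in the treatment termination (visit 6) and safety visits (visit 7) will be performed at this visit". It then says "If a subject refuses to take part in the scheduled study visits and activities it will be documented as early study termination". Section 9.2.11.1 adds that "ETT subjects will be requested to continue with all study visits and activities as planned, for follow up, without taking any study medication".

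**The concern.** Section 6.2 is the only sentence that states a consequence for crossing exclusion 17 or 18 during treatment. It is worded as an instruction, and it stops participation rather than drug. In the definition of EST, stopping study participation covers both treatment and scheduled activities. In 9.2.11.1 it is a step that can follow ETT: "ETT subjects that decided later to stop their participation in the study will be requested to undergo a study termination visit". A site that reads 6.2 in that sense would end the visits of a randomized subject who is willing to continue.

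Two things are at stake. One is the off-drug UPDRS and ESS, which Section 15.6.7 wants collected whether or not treatment has stopped. The other is part of the routine adverse event record, which under the last paragraph of Section 13.2 closes when a subject leaves the study early. These are subjects with worsening organ function, in whom observation off drug is useful.

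**Working it through.** There is no planned figure to reproduce. The check compares the rules and then counts what the literal reading would drop.

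**Comparable stops.** After treatment is stopped, the protocol keeps follow-up going, or asks for it, in each of these cases:

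- intolerable adverse events (5.2)
- failure to reach 1.5 mg of pramipexole ER or placebo (6.1, 7.5)
- confirmed pregnancy (7.5, with visits up to week 14)
- need for rescue medication (10.3)

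No section says why worsening organ function should differ. For moderate renal impairment, the reason given in 6.2 is possible titration above 2.25 mg/day, and stopping the drug already removes that.

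**Inputs for the count.** Nominal days from Appendix I: week 5 = 35, week 8 = 56, week 12 = 84, week 14 = 98. UPDRS II+III and ESS are scheduled after baseline at weeks 5, 8 and 12. Section 15.7 excludes safety data from 30 days after treatment discontinuation. Section 6.1 gives a 7-day tablet down-titration. Assumptions: the stop comes 0 to 7 days after the test visit, routine adverse event recording ends at the stop, and the ±2-day visit windows are ignored.

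**Dropped under the literal reading, per affected subject:**

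| | Week 5 trigger | Week 8 trigger |
|---|---|---|
| Stop day | 35 to 42 | 56 to 63 |
| Scheduled UPDRS/ESS dropped | weeks 8 and 12: 2 of 3 | week 12: 1 of 3 |
| Adverse event recording lost | 98−35 = 63 to 98−42 = 56 days | 98−56 = 42 to 98−63 = 35 days |

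**How much of that falls inside the 30-day window** depends on when discontinuation is taken to occur.

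*Counted from the stop decision:*

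- Week 5 trigger: 30 of the lost days are inside. Week 8 is 56−42 = 14 to 56−35 = 21 days after the stop (inside). Week 12 is 84−42 = 42 to 84−35 = 49 days after (outside), and week 14 is later still.
- Week 8 trigger: 30 of the lost days are inside. Week 12 is 84−63 = 21 to 84−56 = 28 days after (inside). Week 14 is 98−63 = 35 to 98−56 = 42 days after (outside).

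*Counted from the last down-titration tablet (stop day + 7):*

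- Week 5 trigger: last tablet on day 42 to 49. Week 12 is 84−49 = 35 to 84−42 = 42 days later, still outside.
- Week 8 trigger: last tablet on day 63 to 70. Week 14 is 98−70 = 28 to 98−63 = 35 days later. For a stop on day 63 it is 28 days, so week 14 is inside the window.

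**Which analyses use the dropped efficacy data.** Section 15.6.7 defines Week 12/Treatment Termination, for significance testing, as the last visit on study drug. Sections 15.6.9.1 to 15.6.9.4 run the UPDRS sensitivity analyses with or without measurements taken after treatment ended, and the dropped UPDRS visits feed the first version.

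**The case against.** The best defence is that 6.2 is a rationale section and that 7.5 and 9.2.11 govern discontinuation. A stop forced by a laboratory result on a willing subject fits ETT: an investigator's medical reason, an adverse event and patient safety are all listed there. It does not fit a definition of EST built on the subject's request, or the 9.2.11 rule built on refusal. Section 11.1 also speaks of laboratory abnormalities that lead to study drug being discontinued or interrupted, which is drug language. The protocol uses withdrawal from the study loosely elsewhere: 8.5.1 and 12.6 apply it to non-compliance, which 7.5 lists only under ETT, and 13.2 applies it to adverse events, for which 5.2 keeps follow-up going. On this view 6.2 is the same shorthand.

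Much of this stands. The ETT reading is plausible, and many sites may take it. It does not remove the conflict. The passages in 8.5.1, 12.6 and 13.2 leave the decision to judgement, whereas 6.2 is mandatory and tied to tests drawn for that purpose. The EST list also includes adverse events, so a site could find support there. With about 70 sites, two readings are foreseeable.

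The safeguards also stand. The termination visit with all Visit 6 and Visit 7 activities is requested either way. Section 7.5 keeps a subject with a medical reason for withdrawal under the investigator's supervision, although it is worded for one who refuses visits. Sections 11.1 and 13.2 require follow-up of abnormal laboratory findings, and 13.5 requires serious adverse events to be reported for 30 days after the last dose.

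**Conclusion.** The conflict is real but low in priority. Read literally, 6.2 ends scheduled visits that 7.5, 9.2.11 and 9.2.11.1 would keep. The cost per affected subject is 2 of 3 scheduled UPDRS/ESS assessments after a week 5 trigger or 1 of 3 after week 8, and 56 to 63 or 35 to 42 days of routine adverse event recording. The assessment counts are upper limits, because ETT subjects are only asked to continue and UPDRS and ESS are still requested at the termination visit. The number of subjects is not given. Section 6.2 reports no significant renal or hepatic changes in the phase 2b study, so it is probably small.

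Three stronger readings might be inferred, and the documents support none of them:

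- *The primary comparison or its power is harmed.* Significance testing rests on the last on-drug visit, and no rate is given from which a power loss could be derived.
- *These subjects are left without safety follow-up.* The termination visit, laboratory follow-up and serious adverse event reporting remain.
- *After a week 8 trigger only week 12 could have entered the safety analyses.* That holds only if discontinuation is counted from the stop decision. Counted from the last tablet, week 14 can also fall inside the window.

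The day counts rest on the assumed lag of 0 to 7 days and on nominal visit days. The sensitivity analyses are cited as the protocol describes them. Section 15.13 gives the SAP precedence on methods, and only its addendum is available. The addendum concerns subjects who stopped before the week 5 visit and does not bear on this point.

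**What to change.** Replace the instruction in 6.2 with one to this effect: study treatment will be stopped, with tablets down-titrated as in 6.1, and the subject will be handled as ETT under 7.5, 9.2.11 and 9.2.11.1, with scheduled visits continuing unless the subject withdraws consent.

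The cost is one sentence. The ETT pathway, its termination visit and its follow-up visits already exist, so no new procedure is needed.
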